9.8 Multiplicity

No adjustment will be made for multiplicity as there is no formal hypothesis testing.

9.9 Sample Size and Power Calculations

9.9.1 Sample Size and Power for Efficacy Analyses

A secondary objective of the study is to estimate the efficacy of MK-1654 compared to palivizumab as assessed by the incidence of RSV-associated MALRI (outpatient and inpatient) occurring from Days 1 through 150 post Dose 1 in RSV Season 1. The choice of sample size takes into account various factors including difficulties of enrolling this particular population, as well as estimates of efficacy and the associated levels of precision for different sample sizes. Based on the published literature and assumptions listed below, the expected range of efficacy of MK-1654 versus palivizumab is 25% to 40%, and a total sample size of 1000 participants in this study provides reasonable precision around these efficacy estimates.

[Table 8](#) shows the precision for estimating the incidence rate of RSV-associated MALRI in the MK-1654 and palivizumab groups and the precision for estimating the efficacy of MK-1654 relative to palivizumab for RSV-associated MALRI with a sample size of 500 participants per treatment group under the following assumptions:

- RSV-associated MALRI incidence is 15% in this population.
- The attrition rate is 10% in the PPE population.
- In order to estimate the incidence rates of RSV-associated MALRI in the MK-1654 and palivizumab groups, MK-1654 efficacy against RSV-associated MALRI is assumed to be 70% while palivizumab efficacy against RSV-associated MALRI is varied from 45% to 70% in 5% increments based on estimates in the published literature.
- Another scenario is presented where MK-1654 efficacy against RSV-associated MALRI is assumed to be 65% and 60% when the palivizumab efficacy against RSV-associated

MALRI is assumed to be 70% to assess the impact of this assumption on the precision of the efficacy estimates.

Table 8 Precision for Estimating the Efficacy of MK-1654 Relative to Palivizumab Against RSV-associated MALRI

Observed Incidence for MK	Observed Incidence for Pali	Estimate of Efficacy of MK vs. Pali (%)	95% CI for Efficacy of MK vs. Pali (%) ^a	95% CI for MK Incidence ^b	95% CI for Pali Incidence ^b
0.06	0.045	-33.3	(-147.7, 22.0)	(0.040, 0.087)	(0.028, 0.069)
0.0525	0.045	-16.7	(-127.0, 30.7)	(0.034, 0.078)	(0.028, 0.069)
0.045	0.045	0	(-97.1, 42.3)	(0.028, 0.069)	(0.028, 0.069)
0.045	0.0525	14.3	(-62.6, 50.3)	(0.028, 0.069)	(0.034, 0.078)
0.045	0.06	25.0	(-35.9, 56.5)	(0.028, 0.069)	(0.040, 0.087)
0.045	0.0675	33.3	(-17.2, 61.4)	(0.028, 0.069)	(0.046, 0.096)
0.045	0.075	40.0	(-4.6, 64.5)	(0.028, 0.069)	(0.052, 0.105)
0.045	0.0825	45.5	(5.9, 67.3)	(0.028, 0.069)	(0.058, 0.114)
CI=confidence interval; MALRI=medically attended lower respiratory infection; MK=MK-1654; Pali=palivizumab; RSV=respiratory syncytial virus. ^a Based on 1000 simulations from a modified Poisson regression model with a 10% attrition rate. ^b Exact CI for Poisson variable using the Chi-square distribution.					

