4 STUDY DESIGN

4.1 Overall Design

This is a partially blinded, randomized, active-controlled, multi-site study to evaluate the safety, tolerability, and efficacy of MK-1654 versus palivizumab and the PK of MK-1654 in infants who are eligible and recommended to receive palivizumab in their first RSV season. Part 1 of the study will be double-blind, and Part 2 will be open-label (see Section 1.3). A secondary purpose of the study is to evaluate the safety, efficacy, and PK of a dose of MK-1654 administered at the start of the second RSV season (RSV Season 2) for eligible participants in either treatment group who continue to be at increased risk of RSV who are entering their second RSV season (see Section 5.1 and Section 5.2).

The Sponsor estimates that the study will require approximately 5 years from the time that documented informed consent is provided for the first participant until the last participant's last study-related contact or visit.

Overall, 1000 participants will be randomized in a 1:1 ratio to receive MK-1654 or palivizumab on RSV Season 1 Day 1 (double-blind). Randomization will be stratified according to the following factors:

1. Region:

- Northern Hemisphere
- Southern Hemisphere

2. Participant condition (see Section 5.1, Inclusion Criteria #1):

- CLD (≥ 200 infants)
- CHD (≥ 100 infants)
- Neither CLD nor CHD < 29 weeks gestational age
- Neither CLD nor CHD ≥ 29 weeks gestational age

Infants 0 through 8 months (ie, up to 8 months and 29 days) of age at the time of consent will comprise at least 90% of the participants. Enrollment will begin during the 4 weeks before the estimated onset of the RSV season and will end before the estimated peak of the RSV season (approximately a 17-week duration during a routine RSV season; see Section 4.2.1.1.1). Infants born before the RSV season should be enrolled before the onset of the RSV season. Infants born during the RSV season should be enrolled as soon as possible after birth. Special considerations for RSV season determination in tropical and subtropical regions, as well as disrupted RSV seasonality (eg, due to COVID-19), are in the regional RSV seasonality guidance document (or equivalent).

CLD and CHD participants will be eligible and consented for inclusion in 2 RSV seasons. Participants in the Early or Moderate Pre-term Group who meet the additional inclusion criteria for RSV Season 2 (see Section 5.1) will also be consented for participation in 2 RSV seasons.

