9.5 Analysis Populations

9.5.1 Efficacy Analysis Populations

Full Analysis Set (FAS) Population

The FAS population will serve as the primary population for the estimation of efficacy and for the estimation of incidence of RSV-associated disease. The FAS population consists of all randomized participants who receive at least 1 dose of study treatment. Participants will be included in the treatment group corresponding to the study treatment they were randomized to for the analysis using the FAS population.

For an episode of respiratory infection to be considered for evaluation of an efficacy endpoint for the analysis in the FAS population, a PCR result from the study central laboratory must be available for an NP sample that is collected between 0 and 12 days after symptom onset and between 7 days before and 12 days after symptom worsening. A sensitivity analysis will be conducted, which will include PCR results from NP samples collected within the timeframe mentioned above but not tested at the study central laboratory.

Per-Protocol Efficacy (PPE) Population

The PPE population will serve as a supportive analysis population for the estimation of efficacy and incidence of RSV-associated disease. To be eligible for inclusion in the PPE population, study participants must satisfy the following criteria:

- Receive a complete regimen of the correct clinical material corresponding to the treatment group the participants were randomized into (ie, 1 dose of MK-1654 for participants randomized to the MK-1654 group and 3 to 5 doses of palivizumab within the protocol-specified windows for participants randomized to the palivizumab group based on the date of enrollment and the predefined RSV season end date at each site),
- Have at least 1 follow-up visit/contact for assessment of RSV disease,

- Do not undergo 1) ECMO or 2) surgical intervention for CHD requiring cardiopulmonary bypass during the efficacy follow-up period (Day 150 or Day 180), and
- At any time during dosing or efficacy follow-up, do not experience a protocol deviation that may interfere with the assessment of protection against RSV infection conferred by MK-1654.

The final determination on important protocol deviations, and thereby the composition of the PPE population, will be made prior to the final database lock and will be documented in a separate memo.

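### Table 8's efficacy confidence limits are not the modified Poisson interval at the incidences printed beside them, and the summary behind them is not stated; the lower limits read too pessimistic, by 5 to 8 points in the expected efficacy range against a fully followed FAS.

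*Combined protocol and SAP*

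**What the plan says.** Section 4.1: "Overall, 1000 participants will be randomized in a 1:1 ratio". Section 9.9.1 introduces Table 8 as the precision "with a sample size of 500 participants per treatment group", and two of its assumptions matter here: "RSV-associated MALRI incidence is 15% in this population" and "The attrition rate is 10% in the PPE population". It expects efficacy against palivizumab of 25% to 40% and calls the precision around such estimates reasonable.

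Table 8 gives the observed incidence in each arm, the efficacy estimate, a column headed "95% CI for Efficacy of MK vs. Pali", and an interval for each incidence. Footnote a describes the efficacy intervals as "Based on 1000 simulations from a modified Poisson regression model with a 10% attrition rate". Footnote b describes the incidence intervals as "Exact CI for Poisson variable using the Chi-square distribution". Neither the footnotes nor the text says how the 1000 simulated intervals were reduced to one pair of limits.

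Section 9.5.1: "The FAS population will serve as the primary population for the estimation of efficacy". The FAS is every randomized infant who received at least one dose; the PPE is supportive. Section 9.6.1 specifies modified Poisson regression with robust variance and a log follow-up offset, so infants with incomplete follow-up still contribute person-time.

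**The concern.** Each row of Table 8 looks like the result of one trial: two observed incidences, their exact ratio as an efficacy, and that estimate's confidence interval. A modified Poisson interval is built on the log rate-ratio scale, so the estimate should sit at its log midpoint. In the printed rows it does not, which means that no trial observing those incidences would report that interval.

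The population is also unclear. The text says 500 per group, the attrition assumption belongs to the PPE, and the primary efficacy set is the FAS, for which no interval is given. Table 8 is the quantitative support for the precision claim on the first secondary endpoint, so a reader needs to know what its limits represent.

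**Working it through.** **Inputs.** Arm incidences, printed estimates and limits: Table 8. Randomized n = 500 per arm: Sections 4.1 and 9.9.1. PPE n = 500 × 0.90 = 450. z = 1.96. Model: Section 9.6.1.

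**1. Which n lies behind the table.** The exact Poisson interval for incidence 0.06 is 0.0395 to 0.0873 at 450 and 0.0405 to 0.0857 at 500. The table prints 0.040 to 0.087. The incidence columns reproduce to three decimals only at 450.

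**2. Symmetry check, from printed numbers alone.** Log midpoint as efficacy = 100 × {1 − √[(1 − L/100)(1 − U/100)]}. For the row at -16.7%: √(2.270 × 0.693) = 1.254, so the midpoint is -25.4%. At 0%: √(1.971 × 0.577) = 1.066, midpoint -6.6%. The rows at -33.3%, 14.3% and 25.0% give -39.0%, 10.1% and 23.1%.

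**3. Reproducing the printed column.** Binomial counts were drawn at the tabulated incidences with 450 per arm, the robust limits computed for each trial, and the limits averaged on the efficacy scale. The mean limits, in table order, are (-150.7, 21.1), (-123.0, 32.2), (-95.6, 43.1), (-61.6, 50.3), (-37.7, 55.9), (-19.8, 60.4), (-6.0, 64.0) and (5.0, 67.0). Every printed limit is within about 3 Monte Carlo standard errors of these, taking the error of a 1000-run mean. The joint misfit on 16 degrees of freedom is 30.8 at 450 per arm, against 954 at 475 and 3996 at 500. Medians, log-scale means and percentiles of the estimate fit worse.

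**4. The interval at the stated incidences.** SE(log RR) = √(1/x₁ + 1/x₂ − 2/n), with x = n × incidence; limits = 100 × {1 − RR × exp(±1.96 × SE)}. A fitted Poisson model with robust variance gave the same SE (0.2735) on a test data set. Worked row, 40% efficacy at n = 500: x₁ = 22.5, x₂ = 37.5, SE = √(0.04444 + 0.02667 − 0.004) = 0.2591, RR = 0.60. The upper RR limit is 0.60 × exp(0.5078) = 0.997, so the lower efficacy limit is 0.3.

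Lower limits, all rows:

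| Efficacy (%) | Printed | n = 450 | n = 500 | Printed − 450 | Printed − 500 |
|---|---|---|---|---|---|
| -33.3 | -147.7 | -133.7 | -127.1 | -14.0 | -20.6 |
| -16.7 | -127.0 | -108.2 | -102.1 | -18.8 | -24.9 |
| 0 | -97.1 | -82.6 | -77.0 | -14.5 | -20.1 |
| 14.3 | -62.6 | -52.9 | -48.5 | -9.7 | -14.1 |
| 25.0 | -35.9 | -31.5 | -27.7 | -4.4 | -8.2 |
| 33.3 | -17.2 | -15.2 | -12.0 | -2.0 | -5.2 |
| 40.0 | -4.6 | -2.5 | 0.3 | -2.1 | -4.9 |
| 45.5 | 5.9 | 7.8 | 10.2 | -1.9 | -4.3 |

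Upper limits differ from the 500-per-arm form by at most 1.9 points.

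**5. Partial follow-up in the FAS.** The plan gives no figure for person-time lost. If the 10% who drop out contribute half their time, the effective size is about 475 per arm (450 + 25). The lower limits in the 25%, 33.3% and 40% rows are then about -29.5, -13.5 and -1.0.

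**6. What makes up the largest gap.** In the -16.7% row: 500 to 450 per arm moves the limit from -102.1 to -108.2 (about 6 points); averaging skewed limits moves it to -123.0 (about 15); the remaining 4 points, to the printed -127.0, are consistent with Monte Carlo error in 1000 runs.

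**The case against.** The column can be defended. Footnote a discloses both the simulation and the attrition, and the figures reproduce closely under that method, so no slip of calculation is shown. A mean of simulated limits is a recognised measure of expected precision, and the symmetry check applies to a single fitted interval, not to an average of many. Sizing on the smaller PPE set is openly stated and cautious, and the PPE is a planned analysis of this endpoint. On the table's own 450 basis, interval widths in the expected range differ by only 3 to 4% (92.4 against 88.7 points at 25% efficacy). The averaging explanation is also inferred: it is clearly the best of the variants tried, but the joint fit is not perfect (p about 0.01), and the actual simulation may have included covariates.

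All of that stands, and it limits the point. It does not answer two things. The summary is not named, although it sits beside columns headed as observed values and an estimate that was not simulated. And the primary population has no interval.

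A reader might infer that Table 8 is wrong by up to 25 points. The documents do not support that: the figure comes from a scenario with MK-1654 worse than palivizumab, and it adds three separate effects. A reader might also infer that the trial is wrongly sized. It does not follow: there is no hypothesis test, Section 9.9.1 cites enrolment difficulty among other reasons for N, Section 9.9.2 covers safety precision separately, and every discrepancy in the lower limit is in the pessimistic direction.

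**Conclusion.** The point holds as one of presentation and labelling with a measurable effect. The printed lower limits are lower than the planned model would give at the tabulated incidences in every row. In the range the sponsor expects, the difference is 2 to 4 points at 450 per arm and 5 to 8 points at 500. Correction makes the precision claim slightly stronger.

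The comparison at 500 per arm assumes full FAS follow-up and an unadjusted model. The true FAS interval should lie somewhat closer to print. In particular, excluding zero at 40% efficacy depends on full follow-up and should not be relied on. That the printed limits are not the interval at the stated incidences follows from Table 8 itself; that they are arithmetic means of simulated limits is the best available explanation, not something the plan states.

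**What to change.** Replace the efficacy CI column with the interval at the stated incidences: the closed form, or the median or log-scale mean of simulated limits. State in footnote a which summary is used. Show the interval for the primary FAS, with dropouts contributing partial person-time through the offset and the follow-up assumption written down, next to the 450-per-arm PPE interval. Say in the text which population each column and the 500-per-group statement refer to.

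The cost is a rerun of one table and a reworded footnote. The sample size, endpoints and analysis methods stay as they are.

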9.9.2 Sample Size and Power for Safety Analyses

A total of 1000 participants will be randomized in a 1:1 ratio to receive either MK-1654 and placebo or palivizumab in RSV Season 1. The probability of observing at least 1 SAE in this study depends on the number of participants dosed and the underlying percentage of participants with a SAE in the study population. Calculations below assume that 100% of the randomized participants will be evaluable for safety analyses. There is an 80% chance of observing at least 1 SAE among 500 participants in the MK-1654 group if the underlying incidence of a SAE is 0.33% (1 of every 303 participants receiving MK-1654). There is a 50% chance of observing at least 1 SAE among 500 participants in the MK-1654 group if the underlying incidence of a SAE is 0.14% (1 of every 714 participants receiving MK-1654). If no SAEs are observed among the 500 participants in the MK-1654 group, this study will provide 97.5% confidence that the underlying percentage of participants with a SAE is <0.74% (1 in every 136 participants in the MK-1654 group).

9.10 Subgroup Analyses

Subgroup analyses based on the following subgroups will be performed for selected safety and efficacy endpoints: (1) Southern Hemisphere and Northern Hemisphere regions and (2) participant condition (CLD, CHD, neither CLD nor CHD <29 weeks gestational age, and neither CLD nor CHD ≥29 weeks gestational age).

9.11 Compliance (Medication Adherence)

The number and proportion of randomized participants receiving each dose will be summarized (see Section 9.12).

9.12 Extent of Exposure

The extent of exposure will be summarized by the number and proportion of randomized participants administered MK-1654, placebo, or palivizumab per dosing schedule.

10 SUPPORTING DOCUMENTATION AND OPERATIONAL CONSIDERATIONS

10.1 Appendix 1: Regulatory, Ethical, and Study Oversight Considerations

10.1.1 Code of Conduct for Clinical Trials

Merck Sharp & Dohme LLC, Rahway, NJ, USA (MSD)

Code of Conduct for Interventional Clinical Trials

I. Introduction

A. Purpose

MSD, through its subsidiaries, conducts clinical trials worldwide to evaluate the safety and effectiveness of our products. As such, we are committed to designing, implementing, conducting, analyzing, and reporting these trials in compliance with the highest ethical and scientific standards. Protection of participants in clinical trials is the overriding concern in the design and conduct of clinical trials. In all cases, MSD clinical trials will be conducted in compliance with local and/or national regulations (including all applicable data protection laws and regulations), and International Council for Harmonisation Good Clinical Practice (ICH-GCP), and also in accordance with the ethical principles that have their origin in the Declaration of Helsinki.

B. Scope

Highest ethical and scientific standards shall be endorsed for all clinical interventional investigations sponsored by MSD irrespective of the party (parties) employed for their execution (e.g., contract research organizations, collaborative research efforts). This Code is not intended to apply to trials that are observational in nature, or which are retrospective. Further, this Code does not apply to investigator-initiated trials, which are not under the full control of MSD.

II. Scientific Issues

A. Trial Conduct

1. Trial Design

Except for pilot or estimation trials, clinical trial protocols will be hypothesis-driven to assess safety, efficacy and/or pharmacokinetic or pharmacodynamic indices of MSD or comparator products. Alternatively, MSD may conduct outcomes research trials, trials to assess or validate various endpoint measures, or trials to determine patient preferences, etc.

The design (i.e., participant population, duration, statistical power) must be adequate to address the specific purpose of the trial and shall respect the data protection rights of all participants, trial site staff and, where applicable, third parties. All trial protocols are and will be assessed for the need and capability to enroll underrepresented groups. Participants must meet protocol entry criteria to be enrolled in the trial.

2. Site Selection

MSD's clinical trials are conducted globally in many different countries and in diverse populations, including people of varying age, race, ethnicity, gender, and accounting for other potential disease related factors. MSD selects investigative sites based on medical expertise, access to appropriate participants, adequacy of facilities and staff, previous performance in clinical trials, as well as budgetary considerations. Prior to trial initiation, sites are evaluated by MSD personnel (or individuals acting on behalf of MSD) to assess the ability to successfully conduct the trial.

Where appropriate, and in accordance with regulatory authority guidance, MSD will make concerted efforts to raise awareness of clinical trial opportunities in various communities. MSD will seek to engage underrepresented groups and those disproportionately impacted by the disease under study. MSD will

support clinical trial investigators to enroll underrepresented groups and expand access to those who will ultimately use the products under investigation.

3. Site Monitoring/Scientific Integrity

Investigative trial sites are monitored to assess compliance with the trial protocol and Good Clinical Practice (GCP). MSD reviews clinical data for accuracy, completeness, and consistency. Data are verified versus source documentation according to standard operating procedures. Per MSD policies and procedures, if potential fraud, scientific/research misconduct, privacy incidents/breaches or Clinical Trial-related Significant Quality Issues are reported, such matters are investigated. When necessary, appropriate corrective and/or preventative actions are defined and regulatory authorities and/or ethics review committees are notified.

B. Publication and Authorship

Regardless of trial outcome, MSD commits to publish the primary and secondary results of its registered trials of marketed products in which treatment is assigned, according to the pre-specified plans for data analysis. To the extent scientifically appropriate, MSD seeks to publish the results of other analyses it conducts that are important to patients, physicians, and payers. Some early phase or pilot trials are intended to be hypothesis-generating rather than hypothesis testing; in such cases, publication of results may not be appropriate since the trial may be underpowered and the analyses complicated by statistical issues such as multiplicity.

MSD's policy on authorship is consistent with the recommendations published by the International Committee of Medical Journal Editors (ICMJE). In summary, authorship should reflect significant contribution to the design and conduct of the trial, performance or interpretation of the analysis, and/or writing of the manuscript. All named authors must be able to defend the trial results and conclusions. MSD funding of a trial will be acknowledged in publications.

III. Participant Protection

A. Regulatory Authority and Ethics Committee Review (Institutional Review Board [IRB]/Independent Ethics Committee [IEC])

All protocols and protocol amendments will be submitted by MSD for regulatory authority acceptance/authorization prior to implementation of the trial or amendment, in compliance with local and/or national regulations.

The protocol, protocol amendment(s), informed consent form, investigator's brochure, and other relevant trial documents must be reviewed and approved by an IRB/IEC before being implemented at each site, in compliance with local and/or national regulations. Changes to the protocol that are required urgently to eliminate an immediate hazard and to protect participant safety may be enacted in anticipation of ethics committee approval. MSD will inform regulatory authorities of such new measures to protect participant safety, in compliance with local and/or national regulations.

B. Safety

The guiding principle in decision-making in clinical trials is that participant welfare is of primary importance. Potential participants will be informed of the risks and benefits of, as well as alternatives to, trial participation. At a minimum, trial designs will take into account the local standard of care.

All participation in MSD clinical trials is voluntary. Participants enter the trial only after informed consent is obtained. Participants may withdraw from an MSD trial at any time, without any influence on their access to, or receipt of, medical care that may otherwise be available to them.

C. Confidentiality

MSD is committed to safeguarding participant confidentiality, to the greatest extent possible, as well as all applicable data protection rights. Unless required by law, only the investigator, Sponsor (or individuals acting on behalf of MSD), ethics committee, and/or regulatory authorities will have access to confidential medical records that might identify the participant by name.

D. Genomic Research

Genomic research will only be conducted in accordance with a protocol and informed consent authorized by an ethics committee.

IV. Financial Considerations

A. Payments to Investigators

Clinical trials are time- and labor-intensive. It is MSD's policy to compensate investigators (or the sponsoring institution) in a fair manner for the work performed in support of MSD trials. MSD does not pay incentives to enroll participants in its trials. However, when enrollment is particularly challenging, additional payments may be made to compensate for the time spent in extra recruiting efforts.

MSD does not pay for participant referrals. However, MSD may compensate referring physicians for time spent on chart review and medical evaluation to identify potentially eligible participants.

B. Clinical Research Funding

Informed consent forms will disclose that the trial is sponsored by MSD, and that the investigator or sponsoring institution is being paid or provided a grant for performing the trial. However, the local ethics committee may wish to alter the wording of the disclosure statement to be consistent with financial practices at that institution. As noted above, all publications resulting from MSD trials will indicate MSD as a source of funding.

C. Funding for Travel and Other Requests

Funding of travel by investigators and support staff (e.g., to scientific meetings, investigator meetings, etc.) will be consistent with local guidelines and practices.

V. Investigator Commitment

Investigators will be expected to review MSD's Code of Conduct as an appendix to the trial protocol, and in signing the protocol, agree to support these ethical and scientific standards.

